3.3 Duration of Participation and Overview of What is Expected from Participants

Participants will complete up to a seven week study consisting of screening period, baseline period, up to a 21-day product use period with a total of 9 product use sessions. Screening assessments, baseline questions, product use period questionnaires, adverse event reporting, and end of study experience survey data will be collected. This study will be conducted remotely and will use a web-based data collection platform, Consumer Health Learning and Organizing Ecosystem (Chloe), by People Science where participants will complete study assessments using the Chloe app during the course of the study. Participants will receive the study product during the baseline period. Demographic and medical history data will be collected for the study.

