9.1 Sample Size Estimation and Justification

We anticipate screening up to 100 individuals to achieve a final sample size of approximately 50 evaluable participants. To measure our primary outcome, a single question 10-point visual analogue rating scale (VAS) will be used to reflect motivation after consumption of the Study Product, THC-Only Product, or Placebo. . The average difference in VAS responses between these 3 groups will be measured and analyzed.

Up to 20 post-product use questions, and up to 15 daily survey questions will be collected to reflect any changes in motivation, level of energy, focus, and appetite during the study period. The average difference in responses between Study Product, THC-Only Product, and Placebo will be measured and analyzed as secondary outcomes.

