9.6 Statistical Analysis Plan

The primary objective of this study is to determine the impact of Phylos’ study product on motivation as measured by the change in VAS scores from approximately 50 participants. Univariate statistics will be generated to describe the distribution of patient characteristics and outcome data. Continuous variables will be described using means, standard deviations, minimums and maximums while categorical variables will be described using counts and percentages. VAS scores will be compared from baseline pre-product use; and at end of study (post-product use) of the same individuals. We will analyze up to 58 participants to achieve at least 90% power to detect a mean change in VAS scores of 1 point (SD=2) from baseline with a type I error of 0.05 (two-sided) assuming a paired means dependent Wilcoxon Signed-Rank test. We are testing the null hypothesis that there is no difference between pre-product use and post-product use mean VAS scores within study participants. Summary statistics will be generated, and paired differences between pre-product use and post-product use VAS scores will be reported, along with 95% confidence intervals.

Additionally, parametric linear mixed models will be employed to simultaneously account for correlated observations and adjust for confounding variables (Proc Mixed, SAS). Several covariance structures, including compound symmetry and unstructured, will be evaluated by comparing AIC and BIC to identify optimal model fit. Random slope and intercept will also be considered in a similar manner. Patient characteristics (i.e. age and sex) will be included in adjusted models a priori for confounding control. Directed acyclic graphs will be employed to select other potential confounding variables and identify biases during the model fitting process. Large differences will be further examined and may help identify where further calibration of estimation models are needed.

Stratified and interaction analyses will be employed to detect between-subgroup differences in outcomes. Specifically, we will test the difference in VAS score change between Study Product, THC-Only Product, and Placebo groups. Testing of these differences will be conducted by including 2-way product terms between the exposure and covariate of interest in linear mixed modeling. A significant interaction will be defined by an interaction coefficient with a p-value < 0.05.

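### The mixed models in section 9.6 have no small-sample correction; if a nine-session unstructured covariance is fitted and selected, product tests at about 50 participants reject roughly 10-15% of the time under no effect, not 5%

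*Combined protocol and SAP*

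**What the plan says.** Section 9.6 of the combined protocol and SAP powers the study on a paired comparison of baseline with end of study, "with a type I error of 0.05 (two-sided) assuming a paired means dependent Wilcoxon Signed-Rank test". It then adds linear mixed models in Proc Mixed, adjusted for age and sex. On their covariance it says "Several covariance structures, including compound symmetry and unstructured, will be evaluated by comparing AIC and BIC to identify optimal model fit"; random slopes and intercepts are to be considered in the same way. The differences between Study Product, THC-Only Product and Placebo, and the subgroup interactions, are to be tested in these mixed models, with an interaction called significant at p below 0.05.

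Section 3.3 plans "up to a 21-day product use period with a total of 9 product use sessions", and the study calendar (section 4.0) puts a survey after each session. Section 9.1 expects "a final sample size of approximately 50 evaluable participants". Section 1.0 words the primary endpoint as a change in an average score.

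No section names a denominator degrees-of-freedom method or a small-sample correction. None says whether the model takes nine session values or three period averages per person.

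**The concern.** Model-based standard errors from a mixed model treat the estimated covariance matrix as if it were known. That does little harm when a few parameters are estimated from many people. It matters when the number of covariance parameters approaches the number of participants, as in a nine-session unstructured fit here. The standard errors are then too small, the confidence intervals too narrow and the p-values too low, even if the covariance structure is adequate.

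This affects more than a side analysis. The Wilcoxon test in 9.6 compares baseline with end of study, whereas the primary endpoint in section 1.0 contrasts cannabinoid sessions with placebo sessions. The mixed model is the only method that 9.6 describes for comparing the three products with one another.

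**Working it through.** **Inputs from the documents.** Nine sessions in three periods (3.3, 4.0); about 50 evaluable participants (9.1); up to 58 analysed, a 1-point change, SD 2, two-sided 0.05 and at least 90% power (9.6); adjustment for age and sex (9.6); three products compared (9.6).

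**The plan's own figure.** For a paired comparison, n = (SD × (z₀.₉₇₅ + z₀.₉₀) / δ)² = (2 × (1.960 + 1.282) / 1)² = 42.03, so 43. The exact t calculation gives 44. Dividing 43 or 44 by a Wilcoxon relative efficiency of 0.955 gives 46 or 47; dividing 44 by the lower bound of 0.864 gives 51. Simulated Wilcoxon power is 92.3% at 50 and 95.7% at 58. The statement "We will analyze up to 58 participants" "to achieve at least 90% power to detect a mean change in VAS scores of 1 point (SD=2") is therefore met. The documents state no error rate for the mixed-model product tests.

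**Covariance parameters.** An unstructured matrix of dimension k has k(k+1)/2 parameters.
- Session as unit: 9 × 10 / 2 = 45.
- Period average as unit: 3 × 4 / 2 = 6.
- Compound symmetry: 2.

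**Simulation with no product effect.** There were 4,000 runs per setting (Monte Carlo standard error about 0.5 percentage points), with six balanced sequences, complete normal data, fixed effects for product, session, age and sex, and REML. The true covariance was compound symmetry, period-clustered, AR(1) with 0.7, or AR(1) with rising SD. The table gives uncorrected rejection rates for the nine-session unstructured model; ranges are over the true covariances simulated (at n = 58, compound symmetry only, with the range over reference distributions).

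| Test | n | Reference | Rejects |
|---|---|---|---|
| One product contrast | 50 | normal | 10.6-11.9% |
| One product contrast | 50 | t, n−3 df | 9.9-11.3% |
| 2-df product test | 50 | chi-square | 14.4-15.6% |
| 2-df product test | 50 | F, within-subject df | 14.2-15.3% |
| 2-df product test | 50 | F, n−3 df | 12.7-13.6% |
| One product contrast | 58 | t or normal | 9.6-10.5% |
| 2-df product test | 58 | F or chi-square | 11.8-12.9% |

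The product-by-sex interaction at n = 50 rejects 10.5-11.3% per coefficient and 13.1-15.2% on 2 df. Changing the degrees of freedom does not cure the problem, because the standard error itself is too small.

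**Arithmetic check.** Further simulations with equal participant, period and session variances put the mean standard error 17-20% below the true one. If the standard error is a fraction f of its true value, a nominal 5% normal test rejects 2Φ(−1.96 f). For f = 0.83 this is 10.4%; for f = 0.80 it is 11.7%. Both agree with the contrast rates above.

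**Other readings of the plan, n = 50.**
- One value per period, unstructured, uncorrected: the 2-df test rejects 6.4-7.7%.
- Compound symmetry true and selected, nine sessions: 5.0%.

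**With Kenward-Roger, n = 50, 2-df test.**
- Nine sessions, unstructured: 6.3-7.5%.
- One value per period, unstructured: 5.1%.

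**Selection.** With only compound symmetry and unstructured competing, AIC chose unstructured in anything from 0% of runs (true compound symmetry) to 100% (AR(1)), depending on the covariance assumed. AIC and BIC often disagreed: 70% against 0% in the period-clustered case. In a rough check of 40 runs per setting, adding a period-level random effect that matched the simulated data cut selection of unstructured to 0% by both criteria.

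**The case against.** A reader might infer that the planned product tests simply have a false positive rate of 10% or more. The documents do not support that. Three conditions are needed: the session is the repeated unit, unstructured is selected, and the analyst applies no correction. Section 9.6 permits all three and fixes none. The average-score wording in sections 1.0 and 9.1 makes a three-value model at least as natural, and there the inflation is slight.

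A reader might also infer that AIC will nearly always choose unstructured. That result appears only under particular variance shares and a two-candidate contest. The plan gives no variance shares, speaks of several structures plus random effects, and gives no rule for when AIC and BIC disagree. No selection rate should be claimed.

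Third, the phrase "with a type I error of 0.05 (two-sided") belongs to the Wilcoxon test, so the powered analysis is untouched. That is correct. The only 0.05 threshold stated for the mixed models concerns interactions. The mixed models nevertheless carry the comparison of the three products, so calling them additional does not dispose of the point.

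Finally, Kenward-Roger is not a complete remedy. It leaves some inflation in the nine-session model and does nothing for misspecification: where compound symmetry was false but fitted, the 2-df test rejected 24-27%. This objection stands, and it is why the fix should also name the repeated unit.

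**Conclusion.** The point holds as a conditional one. If a nine-session unstructured model is fitted, selected and left uncorrected at about 50 participants, a product contrast rejects about 10-12% and the 2-df product test about 13-15% under no effect. At 58 participants the rates are only slightly lower. Under the other readings the excess is small or absent.

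The figures assume normal, complete data, balanced sequences and the covariance shapes listed; none of these is given in the documents. Missing sessions, random slopes and other candidate structures are not covered by the error rates. The change is worth making because it is cheap and bears on the only product comparison that 9.6 describes.

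**What to change.** Add to section 9.6: 'All mixed models use REML with the Kenward-Roger adjustment of standard errors and denominator degrees of freedom (DDFM=KR), whichever covariance structure is selected.' Add a second sentence saying whether the repeated unit is the session or the period average. The period average fits the endpoint wording, and with it Kenward-Roger brings the test close to 5%. If sessions are kept, the SAP should acknowledge that some inflation remains. Neither sentence guards against a wrongly chosen compound symmetry, so the rule for choosing the structure needs its own attention.

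The cost is one SAS option and two sentences, with no new data. Intervals become somewhat wider: with nine sessions and an unstructured matrix, Kenward-Roger raised the standard error by about 17% in simulation.

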1.0 OBJECTIVES AND ENDPOINTS

| Objectives | Endpoints/ Measurements |
|---|--|
| Primary Objective | |
| To observe the effect of various cannabinoid-containing products on motivation. | Change in average motivation score by 1 point as measured by a 10-point visual analogue rating scale (VAS) collected between the cannabinoid products and placebo use sessions. |
| Secondary Objective | |
| To observe the effect of cannabinoid products on energy level, focus, and appetite. | Change in average score by 1 point as measured by a 10-point visual analogue rating scale (VAS) between the cannabinoid products and placebo use sessions. |
| Exploratory Objective | |
| To observe changes in overall symptoms and quality of life. To identify improvements for future participant centered study designs using participant feedback. | Changes in overall symptoms and quality of life to be assessed based on MEFA questionnaire responses. Evaluation of study participant experiences based on the experience survey. This may include design and use of app-based data collection tools. |

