4.0 STUDY ACTIVITY CALENDAR

Table 4.1 Study Calendar

| Protocol Activities | Screening ^(a) | Baseline ^(b) | Study Duration | | | | | | | | |
|---|--------------------------|-------------------------|---|-----------------------|------------------------------------|---|-----------------------|------------------------------------|---|-----------------------|---|
| | | | Product Use Period 1 ^(c) (Up to 7 Days) | | | Product Use Period 2 ^(c) (Up to 7 Days) | | | Product Use Period 3 ^(c) (Up to 7 Days) | | |
| | Up to Day -14 | Up to Day 14 | Product Use Session 1 | Product Use Session 2 | Product Use Session 3 / Cross-Over | Product Use Session1 | Product Use Session 2 | Product Use Session 3 / Cross-Over | Product Use Session1 | Product Use Session 2 | Product Use Session 3 / End of Study ⁽ⁱ⁾ |
| Informed Consent | X | | | | | | | | | | |
| Medical History | X | | | | | | | | | | |
| Demographics | X | | | | | | | | | | |
| Concomitant Medications | X | | | | | | | | | | |
| Eligibility Confirmation | X | | | | | | | | | | |
| Product Delivery Receipt | | X | | | | | | | | | |
| Randomization ^d (Study Product, THC Only Product, or Placebo Group) | | X | | | | | | | | | |
| MEFA Questionnaire ^e | | X | | | X | | | X | | | X |
| Daily Product Use Survey ^f | | | X | X | X | X | X | X | X | X | X |
| Adverse Event Survey ^g | | | X | X | X | X | X | X | X | X | X |
| Cross-Over ^h (Study Product, THC Only, or Placebo Group) | | | | | X | | | X | | | |
| Experience Survey | | | | | | | | | | | X |

- a. Screening activities to occur within 14 days prior to Baseline (Day -14).
- b. Baseline activities to occur up to 14 days prior to study product use sessions (Day 14).
- c. Study duration to take place up to 21 days total across 7 days maximum within 3 periods.
- d. Participants to be randomized into the Study Product, THC-Only Product, and Placebo groups for each Product Use Period.
- e. MEFA (Motivation, Energy Level, Focus, and Appetite) Questionnaire to be administered during Baseline and at the end of Product Use 3 sessions.
- f. Daily Product Use Surveys to be administered at the end of each product use session.
- g. Any adverse event occurrence to be reported after the product use session.
- h. Participants cross-over into either Study Product, THC-Only Product, or Placebo group upon completion of Product Use Period 1 and 2.
- i. Participants to complete an experience survey at the end of the study.

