6.0 STUDY PROCEDURES

6.1 Study Overview

Upon initial qualification, the participant will receive an email with study onboarding information including instructions to complete study assessments, as required. These study assessments can be accessed via the Chloe mobile app available on Apple iOS and Android devices. The participant's activities are as follows:

Screening Day -14 to Day 0:

- Complete the Informed Consent
- Complete Demographics, Medical History and Concomitant medications, including current cannabis use information (frequency, route, any previous adverse reactions from taking cannabis and tolerance in taking at least 5mg THC previously)
- Eligibility Confirmation and Enrollment

Baseline Day 1 to Day 14:

- Provide preferred delivery address for product delivery during Baseline
- Random assignment to either Study Product, THC-Only Product, or Placebo Group
- MEFA Questionnaire
- Receipt of study products within 2 weeks of eligibility confirmation
 - Participants will be asked daily if they have received their study product delivery
 - Once they confirm receipt, they will be advised on the product use period start date

Product Use Period (Up to 21 days):

- *The Participant will be randomized into either Study Product, THC-Only Product, or Placebo Group upon enrollment*

- *The Participant will be crossed-over twice into the Study Product, THC-Only Product, or Placebo Group once they have completed 3 product use sessions during the first and second product use periods*
- *The Participant will complete a total of 9 product use sessions between Study Product, THC-Only Product, and Placebo groups across a maximum of 21 days*
- *The Study Product will contain 10mg THCV + 5mg THC in the form of a single gummy.*
- *If the participant cannot tolerate or is not comfortable with 10mg THC based on cannabis use information collected at screening, the participant may opt to cut the gummy in half and be advised to use the same dose for all product use days for the duration of the study.*

Period 1: Up to 7 days

- After 3 product use sessions:
 - Daily survey questions regarding motivation, level of energy, focus and appetite
 - At the end of Period 1:
 - MEFA Questionnaire and Adverse Event Reporting

Crossover:

- Upon completion of Period 1, participants will cross-over to either the Study Product, THC-Only Product, or Placebo group for up to 7 days.

Period 2: Up to 7 days

- After 3 product use sessions:

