9.4 Covariates and Subgroups

Demographic and baseline values will be collected and analyzed on all participants. Data on age, sex, race/ethnicity, medical history including prior cannabis use, medical diagnoses, prescriptions, alcohol use, smartphone operating system (Android or iOS) will all be collected and included in univariate, bivariate, and multivariate analyses. Subgroup analyses will be

conducted to examine differences in outcome by all covariates available.

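### Section 9.6 writes no product-versus-placebo contrast for the primary endpoint and names no period term for a three-period crossover

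*Combined protocol and SAP*

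**What the plan says.** Section 1.0 sets the primary endpoint as a 1-point change in average motivation score on a "10-point visual analogue rating scale (VAS) collected between the cannabinoid products and placebo use sessions". Section 9.1 repeats the intention to compare the three products but gives no model. Each participant takes all three products, one in each of three consecutive periods (Table 4.1 and section 6.1).

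Section 9.6 has three analysis components:

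- A Wilcoxon signed-rank test of baseline against end of study. This is the only test with a power statement.
- Linear mixed models, of which it says "Patient characteristics (i.e. age and sex) will be included in adjusted models a priori for confounding control". Other confounders are to be chosen by directed acyclic graphs, and a random slope and intercept will be considered. The slope variable is not named.
- Stratified and interaction analyses. Here the plan says "Specifically, we will test the difference in VAS score change between Study Product, THC-Only Product, and Placebo groups", and then "Testing of these differences will be conducted by including 2-way product terms between the exposure and covariate of interest in linear mixed modeling". Significance is judged by the p-value of an interaction coefficient.

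Section 9.4 lists further covariates: "Data on age, sex, race/ethnicity, medical history including prior cannabis use, medical diagnoses, prescriptions, alcohol use, smartphone operating system (Android or iOS"). All are person-level. Table 4.1 collects demographics, medical history and medications at screening only. Product use period is not named as a model term anywhere in section 9.

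**The concern.** The endpoint calls for a contrast between products within a person. The only place where a three-product test is specified describes something else, an interaction between product and a covariate. If the Study Product raised motivation equally in everyone, that interaction would be zero however large the benefit. An analyst following the text would have no written test of the primary endpoint and would have to choose one after the data are in.

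The model terms also do not match the design. In a crossover, the factor that varies within a person alongside product is period. Novelty, habituation or growing familiarity with a single-item scale could move ratings from one period to the next. The plan commits to adjusting for age and sex, which cancel from the contrast, and leaves period to later model selection.

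**Working it through.** **The plan's own figure.** Inputs from section 9.6: change 1 point, SD 2 (taken as the SD of the paired change), two-sided alpha 0.05, power at least 90%. The normal formula gives n = ((1.960 + 1.282) × 2 / 1)² = 42.0, and the paired t-test needs 44. Simulated Wilcoxon power is 92% at n = 50 and 95% at n = 58, so the stated power holds. It applies to change from baseline, however. Using SD 2 for product minus placebo is an assumption.

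**What the interaction term tests.** Suppose the product effect is the same in everyone. In 6,000 simulated trials per scenario (n = 50, paired SD 2, period in the model), the product-by-sex or product-by-age coefficient rejects in 4.7% to 5.2% of trials, whether the true effect is 0, 1 or 2 points. The main-effect contrast rejects in 94% at 1 point. The first result follows by construction. It shows what the term measures, not which reading the authors intended.

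**Age and sex.** If b × age and c × sex enter additively, both are subtracted out of a participant's Study Product score minus the same participant's placebo score. In one simulated complete data set of 50, the contrast was 1.4441 (SE 0.2775) with and without them. Section 9.3 requires sessions under every product and section 9.5 restricts regressions to complete cases, so the complete-data condition is nearly secured.

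**Omitting period.** Assumptions: n = 50, one mean per period, paired SD 2, linear drift of d points per period. The way orders are allocated is not described, so two cases are shown. Over the six possible orders, the Study Product minus placebo period gap is −2, −1, −1, 1, 1 or 2, with mean square (4+1+1+1+1+4)/6 = 2.

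- With period in the model: SE = 2/√50 = 0.283 at any d.
- Without period: reported SE = √((4 + 2d²)/50), which is 0.287, 0.300 and 0.346 at d = 0.25, 0.5 and 1.
- Balanced orders: the gaps cancel, so the true SD of the estimate stays at 0.283 and only the reported SE grows.
- Simple randomisation: the mean gap varies by chance with SD √(2/50) = 0.20 period. The true variance becomes 4/50 + 2d²/50, and the reported SE is honest.

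Hand check at d = 1, effect 1 point, 96 df (critical t 1.985). The rejection limit is 1.985 × 0.346 = 0.688.

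- Balanced: power = Φ((1 − 0.688)/0.283) = Φ(1.10) = 86%. Type I error = 2 × (1 − Φ(0.688/0.283)) = 2 × (1 − Φ(2.43)) = 1.5%.
- Simple: power = Φ((1 − 0.688)/0.346) = Φ(0.90) = 82%.

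Simulated power, without versus with period:

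| Drift per period | Balanced orders | Simple randomisation |
|---|---|---|
| 0.5 | 92% vs 94% | 91% vs 93% |
| 1 | 85–86% vs 93% | 81–82% vs 93% |

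The 93% and 94% in the with-period figures are the same value within simulation error. At 0.25 point, balanced, power is 93% either way. Type I error without period under balanced orders is 3.7% at 0.5 point and 1.5% to 2.0% at 1 point. Under simple randomisation it is about 5% throughout.

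**Range for the borrowed SD** (balanced, drift 0.5 then 1):

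- SD 1.5: 99% versus over 99%, then 97% versus over 99%.
- SD 2.5: 78% versus 80%, then 71% versus 80%.

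**No drift.** Including period costs almost nothing: SE 0.284 versus 0.281 under simple randomisation, and 0.282 for both when balanced.

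**The case against.** The strongest reply is that section 9.6 does announce a comparison of the three products, in terms of change in VAS score. If the unnamed covariate is pre/post use, the 2-way term is product by pre/post, and that is a product comparison. This reading is possible and cannot be excluded. But it is not stated, and it sits awkwardly in a paragraph about subgroup differences. Table 4.1 also schedules only one pre-use questionnaire, at Baseline, with none before Period 2 or 3. With a shared baseline B, (Study Product − B) − (placebo − B) = Study Product − placebo. Writing the main-effect contrast therefore loses nothing even if that reading was meant.

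A second reply is that the period loss is small unless drift is large. This stands. At 0.5 point per period power stays above 90% for SD 2, and the notable loss needs 1 point per period, a 2-point shift from Period 1 to Period 3 on a 10-point scale. The graph-based selection step and the unnamed random slope also leave room for time to enter, though they do not ensure it.

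A third reply is that adjusting for age and sex does no harm. That is right. The point is only that it does not do the job given to it.

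**Conclusion.** The point holds in a limited form. The main defect is that the primary endpoint has no written contrast, and the test described for the three products is, on its literal wording, one of effect modification. The missing period term is secondary: negligible at 0.25 point of drift per period, about 2 points of power at 0.5, and about 8 (balanced) to 12 (simple) at 1. These sizes rest on an assumed drift, n = 50 and a paired SD borrowed from the baseline-change power statement.

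Three stronger inferences are tempting and not supported:

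- *That the plan does not intend to compare products.* It says that it will, in sections 1.0, 9.1 and 9.6. The specification is what fails.
- *That omitting period biases the contrast or inflates type I error.* Randomised orders make systematic bias unlikely. Type I error is about 5% under simple randomisation and below 5% with balanced orders.
- *That precision is lost in every case.* With balanced orders the estimate is as precise as before. The reported SE is too large (0.35 versus 0.28 at 1 point) and the test is conservative. Precision is truly lost only under simple randomisation.

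**What to change.** In section 9.6:

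- Specify a linear mixed model with product (three levels) and period (1, 2, 3) as fixed effects and a random participant effect. If session scores rather than period means are modelled, add a participant-by-period random effect.
- Name Study Product minus placebo as the test of the primary endpoint, which matches the objective that opens section 9.6. Name THC-Only minus placebo as a further contrast, since section 1.0 speaks of products in the plural.
- State that the baseline versus end-of-study Wilcoxon test is supportive, so that the section does not hold two unranked primary tests. Adding period to the mixed model does not remove drift from that comparison.
- Keep exposure-by-covariate terms for subgroup analyses only. Age and sex may stay as optional terms.

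The cost is some SAP wording and two degrees of freedom (96 to 94 at n = 50), plus one variance component if session scores are used. The period number follows from the study calendar, so no new data are needed.

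### Interactions are declared significant on any single coefficient at p<0.05, across all available covariates, without a joint test or exploratory label, and the product comparison is worded as an interaction test.

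*Combined protocol and SAP*

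**What the plan says.** Section 9.4 lists eight covariate items: age, sex, race/ethnicity, medical history including prior cannabis use, medical diagnoses, prescriptions, alcohol use and smartphone operating system. It says subgroup analyses will be "conducted to examine differences in outcome by all covariates available".

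Section 9.6 says: "Stratified and interaction analyses will be employed to detect between-subgroup differences in outcomes". The next sentence makes this specific: "we will test the difference in VAS score change between Study Product, THC-Only Product, and Placebo groups". The method follows: "Testing of these differences will be conducted by including 2-way product terms between the exposure and covariate of interest in linear mixed modeling". The decision rule closes the paragraph: "A significant interaction will be defined by an interaction coefficient with a p-value < 0.05".

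Sections 9.4 to 9.7 give no joint test per covariate, short list, multiplicity adjustment or exploratory label for these analyses. The exploratory objective in Section 1.0 covers overall symptoms, quality of life and participant experience, not subgroups.

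**The concern.** There are two separate problems.

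1. **The rule works on single coefficients.** A three-level exposure crossed with a binary or continuous covariate gives two product terms under reference coding, and a multi-level covariate gives more. Calling the interaction significant if either term has p<0.05 allows two chances per covariate, and the rule is then repeated over an unstated number of covariates and possibly outcomes. Section 12.5 says the results will be shared with participants and may inform what they buy, and Section 2.2 says the findings will feed into product formulation. A false subgroup claim therefore has somewhere to go.

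2. **The product comparison is attached to the wrong term.** The primary endpoint in Section 1.0 contrasts cannabinoid products with placebo, whereas the signed-rank test in Section 9.6 compares pre-use with post-use scores. The sentence on testing differences between the three products is the only one in Section 9.6 that says how they will be compared by test, and it leads to product-by-covariate terms. Those terms show whether a product effect varies with, say, age. They do not show whether the products differ.

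**Working it through.** **The plan's own figure.** Section 9.6 gives no familywise error rate for interactions, so there is none to reproduce. Its sample-size statement (1 point, SD 2, two-sided 0.05, at least 90% power, signed-rank test) does reproduce. The paired z formula gives (2 × (1.960 + 1.282) / 1)² = 42.0, so 43, and the exact t calculation gives 44. Dividing by the signed-rank test's relative efficiency gives 44/0.955 = 46.1 for normal data and 44/0.864 = 50.9 in the worst case. About 50 evaluable participants is consistent with that.

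**Inputs for the interaction rule**
- Threshold: 0.05 per coefficient (Section 9.6).
- Products: 3, so 2 coefficients per binary or continuous covariate (Section 9.6).
- Covariates: 8 as listed in Section 9.4, or 5 if diagnoses, prescriptions and alcohol use are read as parts of medical history.
- Outcomes: 1 if motivation only; 4 if energy level, focus and appetite are included (Section 1.0).
- Assumptions: no true interactions, normal approximation, and correlation 0.5 between the two coefficients of one covariate because they share a reference product. Correlations between covariates and between outcomes are not in the documents and are varied below.

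**Per covariate, one outcome.** P(at least one |z| > 1.96 of two, correlation 0.5) = 0.090. Independent coefficients would give 1 − 0.95² = 0.0975.

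**Across covariates, motivation only:** 1 − (1 − 0.0905)^k

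| Covariates k | Chance of at least one false positive |
|---|---|
| 5 | 38% |
| 6 | 43% |
| 7 | 49% |
| 8 | 53% |
| 8, correlated at 0.3 (simulated) | 48% |

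**Four outcomes, independent covariates.** The per-covariate chance that any of 2 × 4 = 8 coefficients has p<0.05 was simulated for three outcome correlations, then carried across covariates:

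| Outcome correlation (assumed) | Per covariate | 5 covariates | 8 covariates |
|---|---|---|---|
| 0.5 | 0.268 | 79% | 92% |
| 0.7 | 0.227 | 72% | 87% |
| 0.9 | 0.166 | 60% | 76% |

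For example, 1 − (1 − 0.268)^8 = 0.92. With 8 × 2 × 4 = 64 coefficients, 64 × 0.05 = 3.2 false positives are expected, whatever the correlation.

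**One joint test per covariate.** The rate per covariate returns to 5%, and eight tests on one outcome give 1 − 0.95^8 = 34%.

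**Power for a real interaction.** Take a 1-point difference in product effect between two subgroups of 25 and borrow the plan's SD of 2. The standard error is √(4/25 + 4/25) = 0.566 and power is 42%. That SD belongs to change from baseline, and the documents give none for a within-person product difference. At SD 1.5 power is 65%, and at SD 2.5 it is 29%.

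**The case against.** - **Scope is inferred.** Section 9.4 promises subgroup analyses by all covariates, while Section 9.6 applies product terms to a covariate of interest that it does not define, and also allows stratified analyses. Stratified summaries could satisfy Section 9.4. This stands: the number of interaction tests is not stated, so the result must be a range.
- **A reader might infer that a false subgroup finding for motivation is more likely than not.** The documents do not support that. It needs eight separate and independent covariates, and the figure falls below 50% with seven, or with eight correlated at 0.3. The healthy-volunteer eligibility criteria may also leave some covariates with little variation. Multi-level covariates push the other way.
- **A reader might infer that the mixed model omits product main effects.** Section 9.6 does not say so. The differences to be tested may be meant as the between-subgroup differences named two sentences earlier, which product terms do test. The wording is ambiguous, but its nearest antecedent is the difference between products, so it needs correcting.
- **Consequence.** No objective concerns subgroups, and subgroup work is often taken as exploratory. The plan does not say that it is, and it sets a formal significance rule.
- **Adjustment costs power.** This is true. Correcting over a short list is a matter of preference, and it lowers power that is already low.

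**Conclusion.** The concern holds within limits. The single-coefficient rule gives about 9% false positives per covariate instead of 5%. If there are no true interactions and covariates are coded as binary or continuous, the chance of at least one false claim is about 38% to 53% for motivation alone. It is roughly 60% to 92% if the rule is applied to all four VAS outcomes, and that range depends on an assumed outcome correlation of 0.5 to 0.9 and on five to eight independent covariates. Even the lowest figure is far above 5%, so the finding does not depend on crossing one half.

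The separate point on wording also holds: as written, Section 9.6 assigns the three-product comparison to terms that test effect modification.

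A reader might take this as inflation of the primary result. It is not: the type I error of the primary paired test does not depend on the interaction rule. This should be corrected before analysis, but it does not undermine the primary test.

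**What to change.** (a) In Section 9.6, test product differences with main-effect contrasts in the mixed model: Study Product versus Placebo, THC-Only versus Placebo, and Study Product versus THC-Only.

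(b) In Section 9.6, replace the single-coefficient rule with one joint F-test of all product-by-covariate terms for each covariate. This controls the rate per covariate, not across covariates, which is why (c) is also needed.

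(c) In Sections 9.4 and 9.6, label all subgroup and interaction analyses exploratory. Report estimates with 95% confidence intervals and the number of tests done. Make no significance claim unless the covariate is on a short list, drawn from covariates already collected and named before data review, with multiplicity adjustment.

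The cost is SAP wording only, with no change to data collection. Fewer subgroup results will carry a significance label. Power for interactions, already low at about 50 evaluable participants, will be lower still for any adjusted test.
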